### **1.1. Study Objectives**

#### **Primary Objective**

The primary objective of this study is to evaluate the long-term safety, tolerability, and effectiveness of lurasidone (20, 40, 60 or 80 mg/day, flexibly dosed) in pediatric subjects who have completed a prior lurasidone study.

### **Secondary Objective**

#### **For all subjects:**

- Proportions of subjects with adverse events (AEs), discontinuations due to AEs, and serious AEs (SAEs).

#### **For subjects continued from Study D1050301, the following will be assessed:**

- Change in Positive and Negative Syndrome Scale (PANSS) total, positive, negative, general psychopathology, and excitability subscale scores;
- Change in the Clinical Global Impression – Severity (CGI-S);
- Change in the Clinician-rated Children's Global Assessment Scale (CGAS);
- Change in the Pediatric Quality of Life Enjoyment and Satisfaction Questionnaire (PQ-LES-Q).

#### **For subjects continued from Study D1050325, the following will be assessed:**

- Change in Aberrant Behavior Checklist (ABC) irritability subscale, and the following subscale scores (hyperactivity, stereotypy, inappropriate speech, and lethargy/social withdrawal);
- Change in the Clinical Global Impression – Severity (CGI-S);
- Change in Children's Yale-Brown Obsessive Compulsive Scales (CY-BOCS) modified for pervasive developmental disorders (PDDs);
- Change in the Caregiver Strain Questionnaire (CGSQ).

#### **For subjects continued from Study D1050326, the following will be assessed:**

- Change in the Children's Depression Rating Scale, Revised (CDRS-R);
- Change in the Clinical Global Impression Bipolar Version – Severity (CGI-BP-S);
- Change in the Clinician-rated Children's Global Assessment Scale (CGAS);
- Change in the Pediatric Quality of Life Enjoyment and Satisfaction Questionnaire (PQ-LES-Q);
- Change in anxiety symptoms as measured by the Pediatric Anxiety Rating Scale (PARS);
- Change in attention-deficit/hyperactivity symptoms as measured by the Attention-Deficit/Hyperactivity Disorder Rating Scale (ADHD-RS) total score.

## **1.2. Study Design**

This is an open-label, 104-week, multicenter, extension study designed to evaluate the long-term safety, tolerability and effectiveness of flexibly dosed lurasidone (20, 40, 60 or 80 mg/day) in

pediatric subjects who have completed a 6-week treatment period in one of the preceding studies, D1050301, D1050325, or D1050326.

Subjects who complete participation in one of the preceding studies, D1050301, D1050325 or D1050326, are eligible for enrollment in this study. Informed consent/assent is obtained from all subjects (where developmentally appropriate) before any study procedures are performed.

Subjects who meet entry criteria transition to this study directly from Study D1050301, D1050325 or D1050326. All subjects are treated with flexibly dosed lurasidone during the trial.

All eligible subjects are treated with lurasidone 40 mg/day for Days 1-7. Beginning with Day 8, dose adjustments (20, 40, 60 or 80 mg/day) are permitted, based on investigator judgment, to optimize tolerability and effectiveness.

Dose adjustment of study drug should occur at the regularly scheduled visits and in increments or decrements of 1 dose level. However, dose reductions for tolerability or safety purposes may occur beginning on Day 2, based on investigator judgment. These dose reductions may be between study visits and at more than 1 dose level at a time (maximum of 2 dose levels at a time). If dose reductions are required between regular study visits, the subject must return to the study site for an unscheduled visit to receive new medication kits and return all used/unused medication kits at the time of dose adjustment.

Safety and effectiveness assessments are conducted at scheduled visits during the study. A follow-up visit occurs 1 week post last dose of study drug.

A Data and Safety Monitoring Board (DSMB) reviews safety and clinical outcome data including data on AEs and SAEs at regular intervals until the D1050301, D1050325, and D1050326 studies are complete and as long as necessary for the D1050302 study, as determined by the Sponsor. The DSMB is independent of the Sponsor, contract research organization (CRO), and the investigators and is empowered to recommend stopping the study due to safety concerns, but not for efficacy or futility.

### **1.2.1. Determination of Sample Size**

Subjects who complete the respective double-blind studies D1050301, D1050325 or D1050326, sign the consent, and meet all entry criteria are included in this study. Studies D1050301, D1050325, and D1050326 have finished, with a total of 271 subjects from D1050301, 125 subjects from D1050325, and 306 subjects from D1050326 enrolling into D1050302. Based on an estimated attrition rate of approximately 30% of subjects over six months, it is expected that at least 100 subjects are to be exposed to lurasidone for a minimum of 6 months for subjects continued from studies D1050301 and D1050325 in study D1050302.

### **1.2.2. Randomization and Blinding**

This is an open-label study, therefore randomization and blinding is not employed.

## **2. ANALYSES PLANNED**

### **2.1. General Analysis Definition**

#### **2.1.1. Logic of Final Database Lock for Adolescent Subjects with Schizophrenia**

Final database lock 1 is expected to occur on June 15, 2018 for subjects who continued from study D1050301 (ie, adolescent subjects with schizophrenia). All data for these subjects will be cleaned and ‘frozen’ prior to the planned database lock (DBL) date and all related parties, including site personnel, clinical research organization (CRO), non-data management (DM) team of the sponsor will be removed access authority of the clinical database for adolescent subjects with schizophrenia. The CSR for adolescent subjects with schizophrenia will be based on the final database lock 1. In case there is a data error identified after the final database lock 1 for adolescent subjects with schizophrenia, depending on the nature of the issue, DM of the sponsor will re-grant the site an access permission to fix the data issue. Errata will be filed as needed and the error will be noted in the final full CSR after the final database lock 2, which will occur after all subjects in study D1050302 complete the study.

#### **2.1.2. Definition of Open-Label Treatment Phase in Extension Study**

The day of the 1st dose date in the extension study will be denoted as study Day 1. All measurements at each visit will be assigned a study day relative to this date. All data collected on/after Day 1 for subjects previously randomized to placebo group in core study or on/after the extension baseline visit for subjects previously randomized to lurasidone groups up to Week 104, including the End-of-treatment/Early Withdrawal visit, will be considered within the open-label treatment phase. That is to say, the start of the open-label treatment period is defined as Day 1 for subjects previously randomized to placebo group and the OL Baseline visit date for subjects previously randomized to lurasidone groups; the end of the open-label treatment phase is defined as the maximum of the last date of administration of study medication and the withdrawal/completion date for subjects who have completed the study.

#### **2.1.3. Visit Windows**

While the Time and Events Schedule of the protocol indicates the visit timing and procedures for each visit, the timing of a subject’s actual visit timing may not be exactly as per the protocol indicated target day/visit window (note that the protocol does not indicate required visit windows, but rather provides clear guidance for visit timing). Consequently, for the purpose of analysis, the conventions outlined below will be used to allocate the data collected at each actual visit to a planned protocol visit by defining analysis visit windows.

The reference day is study Day 1. Definition of baseline and endpoint is provided in [Sections 2.1.5 - 2.1.6](#).

If a subject has 2 or more visits (scheduled or unscheduled) in one analysis visit window, the visit closest to the target day will be used as the study visit for that analysis visit window. The other additional visit(s) in the same analysis visit window will not be included in the by-visit

descriptive summary analyses. However, measurements from this/these other additional visit(s) will be included in the subject listings and in the other safety analyses (eg, Potentially Markedly Abnormal Laboratory Values or the worst case analysis) to assure all on-treatment measurements are included. If 2 study visits occur the same number of days from the target day within the same visit window, the later one will be considered as the study visit for that target day.

Although all (scheduled and unscheduled) visits will be allocated to an analysis visit window, only planned protocol visits for each measurement will be included in the by-visit analyses. All tables and figures presenting data by visit will present only those timepoints where the applicable assessment was scheduled to be collected, unless otherwise noted below. Unscheduled and early termination data will be included for definition of endpoint or overall assessments. Data listings will present all data, regardless of visit.

Table 2 summarizes the analysis visit windows for all questionnaires, laboratory, weight, height, waist circumference, vital signs, ECG, cogstate, tanner stage, menstrual cyclicity, and other safety variables assessed at scheduled visits.

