**Table 2 Time Intervals for Analysis Visit Windows**

Scheduled Visit (label on output in Extension study)	Target Day (a)	Time Interval (Day)
Day 1	1	<=1
Week 2	15	2 – 21
Week 4	29	22 – 35
Week 6	43	36 – 49
Week 8	57	50 - 70
Week 12	85	71 - 98
Week 16	113	99 - 126
Week 20	142	127 - 154
Week 24	169	155 - 182
Week 28	197	183 - 210

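### SAP Table 2 sets the Week 20 target day at 142 where the table's own convention gives 141; the closest-visit rule makes the figure operative, but its effect is very small

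*SAP*

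**What the plan says.** SAP 2.1.2 fixes the origin of the time scale: the first "dose date in the extension study will be denoted as study Day 1". SAP 2.1.3 repeats that "The reference day is study Day 1", and the footnote to Table 2 says the target days are counted from the first dose date.

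The three relevant rows of Table 2 (scheduled visit, target day, interval) read "Week 16 113 99 - 126", "Week 20 142 127 - 154" and "Week 24 169 155 - 182".

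SAP 2.1.3 then uses the target day to choose among records. With two or more visits in a window, "the visit closest to the target day will be used as the study visit for that analysis visit window". On ties: "If 2 study visits occur the same number of days from the target day within the same visit window, the later one will be considered". Visits that are not chosen drop out of the by-visit descriptive summaries but stay in the listings and in the other safety analyses, such as the worst-case tables. The same section adds that "only planned protocol visits for each measurement will be included in the by-visit analyses".

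**The concern.** The Week 20 target does not fit its neighbours. Week 16 is Day 113 and Week 24 is Day 169, 56 days apart, so the midpoint is Day 141 rather than 142.

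In many plans a target day is only a label. Here it decides which of two records is analysed and how ties are broken. A wrong target can therefore put a different record into the Week 20 by-visit tables from the one the rule was meant to select. Protocol 11.4.8 shows what is collected at that visit: vital signs, SAS, BARS, AIMS, and CGI-S or CGI-BP-S, together with a urine drug screen and C-SSRS.

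**Working it through.** **Inputs.** Target days and intervals come from SAP Table 2, and the selection and tie rules from SAP 2.1.3. The ±3-day visit allowance comes from the protocol's schedules of assessments and Section 11.2.

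**1. Convention for the target day.** With Day 1 as the first dose, Week w falls on Day 7w + 1.
- Week 16: 7 × 16 + 1 = 113 (stated 113).
- Week 20: 7 × 20 + 1 = 141 (stated 142).
- Week 24: 7 × 24 + 1 = 169 (stated 169).

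Over all 28 post-Day-1 rows, 27 agree exactly and only Week 20 does not. Counting 7w instead would give 140, so that convention does not produce 142 either.

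**2. Window geometry.** Apart from Week 20, every closed window from Week 12 to Week 100 runs from 14 days before its target to 13 days after.
- Around 141: 141 − 127 = 14 and 154 − 141 = 13, the common pattern.
- Around 142: 142 − 127 = 15 and 154 − 142 = 12, found in no other row.

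The interval fits 141. Only the target is off.

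**3. When the two targets disagree.** Take two visits on Days a < b and target t. The later one is used when |b − t| ≤ |a − t|, which reduces to a + b ≤ 2t.
- t = 141: the later visit is used if a + b ≤ 282.
- t = 142: the later visit is used if a + b ≤ 284.

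The results differ only when a + b is 283 or 284, and then 142 always takes the later visit. For example, with visits on Days 141 and 143, target 141 keeps Day 141; target 142 produces a tie and takes Day 143.

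**4. Share of all day pairs.** Days 127 to 154 are 28 days, so there are 28 × 27 / 2 = 378 pairs. A sum of 283 occurs in 13 and a sum of 284 in 12. That is 25 / 378 = 6.6%.

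**5. Pairs with the scheduled visit on time.** Let the scheduled visit fall on Days 138 to 144 (141 ± 3) and the second visit on any other day of the window: 7 × 27 = 189 pairs. The number that differ, by day of the scheduled visit:
- Days 138, 139, 140 and 141: 2 each, 8 in all. The scheduled visit is the earlier one and 142 displaces it.
- Day 142: 1. Days 143 and 144: 2 each. That makes 5 in all. The scheduled visit is the later one, and 142 keeps it where 141 would drop it.

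The total is 13 / 189 = 6.9%, split into 8 / 189 = 4.2% displaced and 5 / 189 = 2.6% kept.

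**6. Distance between the competing records.** When the sum is 283, the record chosen under 142 is 1 day further from Day 141 than the other; when it is 284, 2 days further.

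**7. Rough count of subjects.** The documents do not say how many subjects have a second visit in this window, so this step rests on assumptions. Taking about 500 subjects still in the study (702 enrolled, less the planned 30% attrition over six months, is 702 × 0.7 = 491), 5% of them with a second visit, and all day pairs equally likely: 500 × 0.05 = 25 subjects, and 25 × 13 / 189 = 1.7. Of these, 25 × 8 / 189 = 1.1 would lose the scheduled visit and 25 × 5 / 189 = 0.7 would keep it. With all 702 subjects the total is 702 × 0.05 × 13 / 189 = 2.4. The count scales directly with the assumed 5%, and is zero if no competing record is eligible.

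**The case against.** The strongest reply is the sentence limiting by-visit analyses to planned protocol visits. Read strictly, an unscheduled record never reaches the Week 20 table and cannot displace a scheduled one. The target would then matter only if two scheduled visits fell in the same window with days summing to 283 or 284. With one of them on schedule, they would be at most 8 days apart (Days 138 and 146), whereas visits at this stage are four weeks apart. That case is practically empty. The reading is fair but not secure, because the selection sentence in the same section expressly takes in both scheduled and unscheduled visits. The text leaves the question open.

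A reader might infer a bias: the protocol requires an unscheduled visit when a dose is reduced between visits for tolerability or safety, so the wrong target could swap on-time visits for visits prompted by side effects. The documents do not support that. The change runs both ways (8 pairs against 5). Not every extra visit need be a tolerability visit. Nothing in the protocol schedules CGI, SAS, BARS or AIMS at an unscheduled visit, and without the assessment there is no competing record.

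A reader might also infer that visits are assigned to the wrong week. They are not: the interval 127 to 154 is correct, and both competing records lie inside it.

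Finally, no main result depends on this figure. The protocol's primary analysis is the incidence of AEs, SAEs and discontinuations due to AEs. PANSS, ABC and CDRS-R are not scheduled at Week 20, and no inferential statistics on effectiveness are planned. This stands, and it limits the importance of the point without making 142 right.

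**Conclusion.** The Week 20 target day is wrong by one day. Both the 7w + 1 rule and the window edges show this from the SAP alone, and the selection rule gives the figure a function.

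The consequence is very small. It is confined to Week 20 by-visit summaries, mainly vital signs, SAS, BARS, AIMS and CGI-S or CGI-BP-S. It needs two eligible records in Days 127 to 154 whose days sum to 283 or 284. The 6.6% and 6.9% are shares of possible day pairs, not of subjects. On the stated assumptions about two subjects are affected, and close to none if unscheduled records are excluded. No systematic bias is shown. Endpoint, Week 52 LOCF and Week 52 Endpoint, the worst-case analyses and the listings do not use this target day, and the C-SSRS tables pool all extension visits.

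**What to change.** Change the Week 20 target day from 142 to 141 in SAP Table 2 and in the visit-window lookup. Leave the interval at 127 to 154.

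The edit is one number, but it is not entirely free. SAP Section 1 states that final database lock 1 took place on June 15, 2018 and that the report for subjects with schizophrenia is complete. The sponsor should check which value was programmed for that lock. If it was 142, the 271 subjects from D1050301 would come under a different Week 20 rule in the full clinical study report, and any Week 20 result that changes should be noted there. If it was 141, only the SAP text needs correcting. Either way the work is a check of one lookup value and, at most, a rerun of the Week 20 columns.

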**Table 2 Time Intervals for Analysis Visit Windows**

Scheduled Visit (label on output in Extension study)	Target Day (a)	Time Interval (Day)
Day 1	1	<=1
Week 2	15	2 – 21
Week 4	29	22 – 35
Week 6	43	36 – 49
Week 8	57	50 - 70
Week 12	85	71 - 98
Week 16	113	99 - 126
Week 20	142	127 - 154
Week 24	169	155 - 182
Week 28	197	183 - 210

**Table 2 Time Intervals for Analysis Visit Windows (Continued)**

Scheduled Visit (label on output in Extension study)	Target Day (a)	Time Interval (Day)
Week 32	225	211 - 238
Week 36	253	239 - 266
Week 40	281	267 - 294
Week 44	309	295 - 322

Week 48	337	323 - 350
Week 52	365	351 - 378
Week 56	393	379 - 406
Week 60	421	407 - 434
Week 64	449	435 - 462
Week 68	477	463 - 490
Week 72	505	491 - 518
Week 76	533	519 - 546
Week 80	561	547 - 574
Week 84	589	575 - 602
Week 88	617	603 - 630
Week 92	645	631 - 658
Week 96	673	659 - 686
Week 100	701	687 - 714
Week 104	729	715 - EOT
(a): Relative to the day of the 1 st dose date		

#### 2.1.4. Pooling Strategy for Analysis of Centers

There will be no pooling of centers in this study.

#### 2.1.5. Definition of Baseline Assessments

The following definitions will be used for effectiveness and safety assessments unless otherwise specified:

- **DB Baseline** (ie, Baseline assessment of the double-blind studies [D1050301, D1050325, or D1050326]): the last assessment made on or before the 1st dose of double-blind study medication as described in the SAPs of the core studies;
- **OL Baseline** (ie, Endpoint assessment of the double-blind studies [D1050301, D1050325, or D1050326] or Baseline assessment of the open-label study [D1050302]): the last assessment made on or before Day 1 of the extension study.

According to the protocol, measurement collected at OL Baseline is same as the value at visit 9 (ie, Week 6) (Study 301/325) or visit 8 (ie, Week 6) (study 326). For operation convenience, the protocol specified that data collected at the EOT visit of the core studies were to be recorded in core studies only and were not to be saved in the clinical database RAVE of the extension study. OL Baseline data in the Study Data Tabulation Model (SDTM) datasets of the study D1050302 will be obtained from corresponding core studies directly.

Unless otherwise specified, at each study visit of study D1050302, data derivation rule and missing imputation method for aggregated parameter that involves multiple individual items (eg, total score, subscale score, or composite score), are same as the corresponding ones in individual core study SAP. DB Baseline is defined same as the Baseline in individual core study per core study SAPs. DB Baseline used in the analysis of study D1050302 will be extracted from corresponding Analysis Data Set (ADS) of the core studies directly unless otherwise specified.

### **2.1.6. Definition of Endpoint Assessments for Final Analysis**

- **Endpoint:** the last post-OL Baseline assessment during the open-label treatment period.
- **Week 52 LOCF/Week 52 Endpoint:** the assessment at Week 52 visit or the last post-OL baseline assessment before the Week 52 visit if the value at the Week 52 visit is missing

Week 52 LOCF will be used to refer effectiveness data only and week 52 Endpoint will be used to summarize safety data. Endpoint will be derived for both effectiveness and safety data.

### **2.1.7. Definition of Aggregated Analysis Timepoint**

Unless otherwise specified, aggregated analysis timepoints will be derived for limited safety assessments (eg, the worst case analysis) as below.

- Any visit in open-label treatment period (extension study): defined as any assessment collected in open-label treatment period.
- Any visit in the first 52 week treatment period (extension study): defined as any assessment collected in the first 52-weeks open-label treatment period (ie, data up to Day 365).

Definition of ‘Any visit in DB treatment period (core study)’ (ie, as any assessment collected in DB treatment period) is same as what were defined in the core studies.

Specifically, above 3 aggregated analysis timepoints in extension study will be generated for the following worst-case analysis:

- Potentially Markedly Abnormal Laboratory Values (PMALV) (Section 2.6.5, Table 3.1)
- Potentially Markedly Abnormal Vital Signs (PMAVS) (Section 2.6.7, Table 7)
- OTc prolongation (Section 2.6.6, Table 4)
- ECG abnormality (Section 2.6.6, Table 5).

See [Sections 2.6.3](#) (Treatment-Emergent Occurrences in OL Period) and [2.6.10](#) (C-SSRS), and [2.6.11](#) UKU for further details about the application of ‘Any visit in DB treatment period (core study)’ and ‘Any visit in open-label treatment period (extension study)’.

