11.2. Standardization of Data Capture

Study Schematic and Schedule of Assessments: A schematic of the study design and summary of assessments to be conducted at each visit are presented in [Figure 1](#) and [Table 3](#), [Table 4](#), and [Table 5](#), respectively.

Assessment Windows: Assessments will be conducted within the time frames specified (ie ± 3 days). All times are relative to the time of dosing for individual subjects

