### **2.1.10. Average Dose and Predominant Dose**

The predominant dose (ie, modal dose, used interchangeably hereafter in this document) in the open-label treatment period is defined as the lurasidone dose to which the subject was exposed for the greatest. If a subject has 2 or more doses with the great duration, the one with higher dosage will be selected as predominant treatment.

The average total daily dose during the open-label treatment phase will be calculated as the sum of the total daily dose divided the treatment duration (see [Section 2.2.2.4](#)). The average total daily dose during a visit period is defined in a similar way.

The predominant dose and average total daily dose in the first 52-weeks period are defined in a similar way; specifically, for a subject, the treatment duration in the first 52-weeks period (in days) is defined to be same as the treatment duration in open-label treatment period if the subject was early terminated by Week 52 visit; otherwise, it is defined as the amount of elapsed time between the first day that study medication was taken and the Week 52 visit date (inclusive).

For any study visit, if medication kit usage information is incomplete (ie, meet one of following conditions: any dispensed medication kit at the visit has missing number of tables returned, or

has missing dosing start or ending date), average total daily dose at the visit will not be derived and will be set as missing. For an assessment period that involves multiple study visits (eg, the open-label treatment period), if at some visit(s) the drug usage information is incomplete, then the other visits with complete information of kit usage will be used to derive the average daily dose and predominant dose accordingly.

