## **Week 52 LOCF/Week 52 Endpoint**

In the event of missing data at Week 52 (per visit window in [Section 2.1.3](#)), the last post-OL baseline observation carried forward approach prior to Week 52 will be used to impute missing values.

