### **2.6.3. Definition of Treatment-Emergent Occurrences in Open-Label Extension Study**

Definition of treatment-emergent adverse event is provided in [Section 2.6.4](#). Treatment-emergent occurrences of adverse reactions, including Potentially Markedly Abnormal Laboratory Values (PMALV), Potentially Markedly Abnormal Vital Signs (PMAVS), and abnormal ECG values, are defined as the assessment values that meet specific safety criteria within the open-label treatment phase (see [Section 2.1.2](#)).

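### The first-52-week worst-case period ends at Day 365, the Week 52 target day, so a Week 52 lab, vital sign or ECG taken on Days 366-378 drops out of its own first-52-week any-occurrence count

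*SAP*

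**What the plan says.** SAP 2.1.7 defines the one-year worst-case period by calendar day: "defined as any assessment collected in the first 52-weeks open-label treatment period (ie, data up to Day 365". It names four analyses that use it: potentially markedly abnormal laboratory values (PMALV), potentially markedly abnormal vital signs (PMAVS), QTc prolongation and ECG abnormality. SAP 2.6.5 to 2.6.7 plan the first-52-week counts and give no other cut-off.

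Other one-year definitions follow the visit:

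- SAP Table 2 gives Week 52 a target of Day 365 and a window of Days 351-378. SAP 2.1.3 explains that windows are needed because "actual visit timing may not be exactly as per the protocol indicated target day/visit window".
- SAP 2.1.6 defines Week 52 Endpoint as "the assessment at Week 52 visit or the last post-OL baseline assessment before the Week 52 visit", the fallback applying when the Week 52 value is missing. The carry-forward rule in SAP 2.1.14 opens "In the event of missing data at Week 52 (per visit window in" and then points to Section 2.1.3.
- SAP 2.1.10 ends the first-52-week dose period, for subjects not terminated by then, at the visit: "the amount of elapsed time between the first day that study medication was taken and the Week 52 visit date (inclusive").
- Protocol 11.2 states "Assessments will be conducted within the time frames specified", given there as plus or minus 3 days.

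SAP 2.6.3 treats treatment-emergent abnormal values as "defined as the assessment values that meet specific safety criteria within the open-label treatment phase". Under SAP 2.1.2 that phase starts on Day 1 for prior-placebo subjects and on "the OL Baseline visit date for subjects previously randomized to lurasidone groups".

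**The concern.** The cut falls inside the Week 52 window. A visit made on schedule, on Days 366-368, is a Week 52 visit for the by-visit row, for Week 52 Endpoint and for the dose period, yet its values are outside the first-52-week worst case. SAP 2.6.6 and 2.6.7 present W52 endpoint and first-52-week occurrence together for QTc, other ECG parameters and PMAVS. A subject whose only prolonged QTc is on Day 367 would appear under W52 endpoint and not under any occurrence in the first 52 weeks. An any-occurrence count could then be smaller than the Week 52 count beside it.

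Labs have less to fall back on. SAP 2.6.5 counts PMALV only for the first 52 weeks and for the overall period, so for most parameters the first-52-week figure is the only one-year count at the PMALV limit.

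Year-one sampling of ECG and labs is also sparse, so losing the Week 52 assessment leaves a long stretch of year one with no scheduled value in the count.

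**Working it through.** **The plan's own figures.** Target day = 7 x 52 + 1 = 365, as in Table 2. Window from midpoints between neighbouring targets: (337 + 365)/2 = 351 and (365 + 393)/2 = 379, giving Days 351-378, as in Table 2.

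**Days excluded by the cut.**
- Protocol tolerance: 365 - 3 = 362 to 365 + 3 = 368, which is 7 days. Days 366-368 fall after the cut: 3 of 7 (43%).
- Whole Table 2 window: 378 - 351 + 1 = 28 days. Days 366-378 fall after the cut: 378 - 365 = 13 of 28 (46%). Days 369-378 lie outside the protocol tolerance.

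**What one late Week 52 visit removes** (visit lists in Protocol 11.4; the blood draws at 6E, 10E and 16E in Protocol Table 9 agree):

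| Measure | Scheduled post-baseline, year one | Share removed | Share removed, prior-lurasidone subject with an OL Baseline value |
|---|---|---|---|
| ECG | Weeks 28, 52 (2) | 1 of 2 | 1 of 3 |
| Labs | Weeks 12, 28, 52 (3) | 1 of 3 | 1 of 4 |
| Vital signs | Weeks 2, 4, 6, 8, then every 4 weeks from 12 to 52 (15) | 1 of 15 | 1 of 16 |

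The last column adds one value because SAP 2.1.2 and 2.6.3 place the OL Baseline visit inside the open-label phase for these subjects. With a late Week 52 visit, the last scheduled ECG and lab inside the period are those of Week 28, target Day 197: 365 - 197 = 168 days (24 weeks) before the cut.

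**PMALV parameters with no other one-year count at the limit.** The criteria table in SAP 2.6.5 lists hematology 7 + chemistry 17 (glucose counted once, prolactin included) + lipids 4 + urinalysis 2 = 30. Table 3.2 gives a by-visit count at the same limit for 4: prolactin at 1 x ULN, HDL-C at 40, LDL-C at 160 and total cholesterol at 240 mg/dL. 30 - 4 = 26.

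**Direction of the effect.**
- Against a period ending at the later of Day 365 and the Week 52 visit date: that period contains the present one for every subject, so the present count is lower or equal.
- Against a period ending simply at the Week 52 visit: no fixed direction. With a visit on Day 355 and an unscheduled abnormal value on Day 362, the Day 365 cut keeps the value and the visit-based period drops it. SAP 2.1.3 brings additional visits into worst-case analyses, so such values can occur. The gap is at most 365 - 351 = 14 days.

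**Mania.** SAP 2.6.4 also plans first-52-week counts of treatment-emergent mania for subjects from D1050326. It gives no end date for them, and 2.1.7 does not list them, so it is open whether a Week 52 YMRS score after Day 365 counts.

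**The case against.** The strongest reply is that a fixed calendar cut is a legitimate definition. Fifty-two weeks is 364 days, so Day 365 already includes the target day, and the SAP states the day openly. Table 2 exists to allocate data to visit rows, while worst-case counts draw on all assessments; one may use a window and the other a date. SAP 2.1.10 concerns dose, a different variable. This stands as far as the cut taken alone. It does not explain why the SAP's one-year columns should disagree on the same value, or why a scheduled Week 52 assessment should be left out.

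The second reply is that no count is shown to change. That is correct: the documents give no distribution of visit days, and a count changes only if a subject's sole qualifying year-one value falls on Days 366-378.

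The third is that the remedy gives subjects unequal periods and alters a definition after final database lock 1. Both are true, and both are costs to be disclosed.

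Four stronger readings are tempting, and the documents do not support them:
- That 3 of 7 or 13 of 28 is the share of subjects affected. These are shares of days.
- That one late visit removes a value from all four counts. Each value affects only its own measure.
- That late abnormal values disappear from safety reporting. They remain in the overall open-label worst case and the listings; QTc, ECG and PMAVS values also remain in the Week 52 and W52 endpoint counts; and labs keep their by-visit summaries and normal-range shifts.
- That the cut biases the counts downward against any visit-based period. The Day 355 and Day 362 example shows otherwise.

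**Conclusion.** The inconsistency is real and minor. As written, a Week 52 value on Days 366-378 is a year-one value in the by-visit row, in Week 52 Endpoint and for the dose period, but not in the first-52-week any-occurrence count for its measure. No other section repairs this. Relative to a period ending at the later of Day 365 and the Week 52 visit, the effect is an undercount or no change, of unknown size. It matters most for ECG (1 of 2 scheduled post-baseline assessments) and for the 26 of 30 PMALV parameters with no other one-year count at their limit. The affected tables are descriptive, no hypotheses are tested, and the primary analysis of AEs, SAEs and discontinuations due to AEs (Protocol 14.7.4.2) is unaffected. The conclusion assumes that the Day 365 limit is programmed literally and that Week 52 visits are allocated by Table 2.

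**What to change.** In SAP 2.1.7, replace the Day 365 limit with: *data up to the later of Day 365 and the date of the Week 52 visit as allocated by Table 2 (at most Day 378)*. State that the same end date applies to the YMRS-based first-52-week mania counts in SAP 2.6.4. Leave 2.1.10 as it is: for late visits the two periods then end on the same date, and for early visits they may still differ by up to 14 days without losing a Week 52 value.

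Rerun the first-52-week PMALV, PMAVS, QTc, ECG and mania tables for the full CSR, which the SAP describes as still to come after final database lock 2. Footnote any difference from the completed schizophrenia CSR, which covers the group of 271 of the 702 enrolled subjects (271 + 125 + 306). The mania tables concern D1050326 only and raise no such difference.

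The cost is one phrase in 2.1.7, one sentence in 2.6.4, one date condition in programming and the reruns. The period becomes subject-specific, running up to 378 - 365 = 13 days past Day 365. A value taken after both Day 365 and the allocated Week 52 visit still counts only in the overall period. Figures for the schizophrenia group may differ between the two reports.
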